### 5.1.1. Subgroup analysis related to primary endpoint

The data on changes to surgical plans will be further analyzed to better understand the changes as described below. This will be done for exploratory purposes and for planning subsequent research.

The comparison between the pre-SPSI™ surgical plan (P1), post-SPSI™ surgical plan (P2) and the actual surgery performed (P3) will be documented on a per-patient and per-level basis. With respect to the influence per-patient, the following table will be completed:

TABLE 4. SUBGROUP ANALYSIS OF THE EFFECTS OF CHANGES TO SURGICAL PLAN ON SURGERIES PERFORMED

Comparison	Proportion of Patients				
	No Change	Increased Levels Fused	Decreased Levels Fused		
P2 versus P1					
P3 versus P2					
P3 versus P1					

### 5.2. **Secondary Endpoint**

#### **Comparison of clinical outcomes in lumbar stenosis patients where surgical planning including SPSI™ compared to historical controls**

After 12 month ( $\pm$  30 days) the change from baseline (12 month minus PreOp) in both the ODI, and the region-specific NRS [46-48] leg pain score will be calculated for each subject in the study. These outcomes instruments have been used in many spine studies, are well-accepted, and there is reference data in the literature that can be used to help interpret results from the proposed study. The secondary endpoint analyses will be done using the per-algorithm population. The per-algorithm population includes all patients where the surgeon modified the initial surgical plan as needed per the algorithm defined in Table 1.

The purpose of the ODI is “To indicate the extent to which a person’s functional level is restricted by disability”. The mean and standard deviation for the 12 month ODI, and the change in the 12 month ODI relative to baseline in study subjects will be compared (using a T-test) to the mean and standard deviations expected from peer-reviewed publications that have randomized lumbar stenosis patients to either decompression only or decompression and fusion. Most of this literature is already available at MMDx but an updated search will be completed using Google Scholar and pubmed prior to the data analysis so that any recent literature can be included. The data analysis will be repeated after 24 month outcomes have been collected.

The comparison of study data to historical control data can be done for each historical control study that has comparable data. The expected rate will be based on a review of the available literature. Many peer-

---

 <https://eprovide.mapi-trust.org/instruments/oswestry-disability-index>

reviewed publications do not report means and standard deviations in a manner that allows for use of their data directly as a historical control [4] although the data can nevertheless help to support choice of numbers to use. Table 5 summarizes some of the studies that provide historical control data.

Most of the prior literature reports a similar improvement in outcome scores for patients treated with decompression only versus decompression and fusion. The null hypothesis is that the use of SPSI™ report by investigators to select levels to treat and the type of surgery to use will NOT effect the improvement in clinical outcomes for lumbar stenosis patients treated with decompression only or decompression plus fusion. The null hypothesis would be rejected if, when SPSI™ is used to select treatment, the improvement in outcome scores is significantly better than reported in the peer-reviewed literature. Although it is unlikely that the sample size in the current study will be sufficient to address the null hypothesis with an acceptable significance level and statistical power, the data from this pilot study will be used to help establish sample sizes required to more definitively document the clinical benefit of SPSI™ for selecting levels and treatments in lumbar spinal stenosis patients.

TABLE 5: A SAMPLING OF PAPERS THAT PROVIDE POTENTIAL REFERENCE ODI AND NRS DATA. A MORE COMPLETE LIST WOULD BE GENERATED PRIOR TO INTERPRETING THE STUDY RESULTS BASED ON A COMPLETE LITERATURE REVIEW AND CONSULTATION WITH THE PARTICIPATING INVESTIGATORS TO ASSURE THAT THE HISTORICAL CONTROL DATA INCLUDE THOSE PUBLICATIONS THAT THE INVESTIGATOR USES TO INFORM PATIENTS ON EXPECTED OUTCOMES.

Study	FU Months	N	Delta ODI		Delta NRS Leg Pain	
			D	D&F	D	D&F
Weinstein 2010	24	109	-16.1(19.8)			
Austevoll	12	260/260	-17.5[16.1]	-19.7[18.3]	-3.0[2.9]	-3.5[2.8]
Ghogawala	12	35/31	-22.2[NR]	-26.1[NR]	NR	NR

Key to abbreviations in Table 5:

Delta ODI: The change in the Oswestry Disability Index at follow-up (FU) relative to PreOp.

Delta NRS Leg Pain: The change in the visual-analog score for patient reported leg pain.

D: Decompression surgery only

D&F: Decompression surgery and fusion surgery

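### Section 5.2 sets one rejection rule for a cohort mixing two operations but fixes no historical study, arm or rule for conflicting results, and neither 12-month row of Table 5 is shown to be both randomized and reported with spreads

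*Combined protocol and SAP*

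**What the plan says.** Section 5.2 applies a t-test to "The mean and standard deviation for the 12 month ODI, and the change in the 12 month ODI relative to baseline in study subjects" in the per-algorithm population. The reference values are the "mean and standard deviations expected from peer-reviewed publications that have randomized lumbar stenosis patients to either decompression only or decompression and fusion". On the choice of study it says "The comparison of study data to historical control data can be done for each historical control study that has comparable data", and it adds that many publications "do not report means and standard deviations in a manner that allows for use of their data directly as a historical control".

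The null hypothesis is that using SPSI "will NOT effect the improvement in clinical outcomes for lumbar stenosis patients treated with decompression only or decompression plus fusion". There is one decision rule, set against published results: "The null hypothesis would be rejected if, when SPSI™ is used to select treatment, the improvement in outcome scores is significantly better than reported". The section states neither alpha nor sidedness.

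On timing, "an updated search will be completed using Google Scholar and pubmed prior to the data analysis so that any recent literature can be included". The Table 5 caption calls the table a sampling and says "A MORE COMPLETE LIST WOULD BE GENERATED PRIOR TO INTERPRETING THE STUDY RESULTS".

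Table 5 has two 12-month rows:
- The 260/260 row: ODI change -17.5 [16.1] for D and -19.7 [18.3] for D&F.
- The 35/31 row: -22.2 for D and -26.1 for D&F, with spreads marked NR.

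The third row is at 24 months. Table 1 (section 1.7) can send a subject to either operation, so the cohort may contain both.

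**The concern.** There is one null and one verdict but several possible comparators. The plan does not say whether the cohort is tested against a D arm, a D&F arm, each arm like with like, or some combination, or what follows if the comparisons disagree. Because the list can be completed after 12-month data exist in a single-arm trial, the comparator can be settled once the cohort's result is knowable.

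The description of the controls also does not fit the table. Section 5.2 describes publications that randomized patients. The 260/260 row, the only 12-month row with spreads, matches by label only reference 26, whose title calls it an observational registry study. The 35/31 row has no spreads, and the section cites reference 4, which matches that row's label, as an example of data that cannot be used directly.

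At stake is whether a claim that outcomes beat the literature rests on the data or on a late choice. That result is also meant to inform the next study.

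**Working it through.** Section 5.2 states no sample size or threshold, so there is no figure of its own to reproduce. What follows is an illustration from the 260/260 row, which is not shown to meet the control description.

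**Inputs.** Table 5: D -17.5, D&F -19.7, 260 per arm. Assumptions:
- The brackets 16.1 and 18.3 are SDs (the table key does not define them).
- n = 59, the analysis number in section 5.5.
- Study SD 17.2, the midpoint of 16.1 and 18.3.
- Two-sided 5%.

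**Cut-offs.** SE = sqrt(17.2²/59 + SD²/260); cut-off = benchmark - 1.96 × SE.
- D: sqrt(5.014 + 0.997) = 2.45; cut-off -17.5 - 4.81 = -22.31.
- D&F: sqrt(5.014 + 1.288) = 2.51; cut-off -19.7 - 4.92 = -24.62.

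| Observed mean change | Welch p against D | Welch p against D&F |
|---|---|---|
| -22 | 0.070 | 0.36 |
| -23 | 0.028 | 0.19 |
| -25 | 0.003 | 0.038 |

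The verdicts differ only inside the band. With n = 65 it is -22.12 to -24.44. A study SD of 15 moves it to -21.8 to -24.1, and an SD of 20 to -23.0 to -25.3. A one-sided 5% test (1.645 × SE) gives -21.5 to -23.8.

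**Like with like.** Split the cohort 30 D and 29 D&F, with each arm 4.4 points better than its benchmark (-21.9 and -24.1). The overall mean is (30 × -21.9 + 29 × -24.1)/59 = -23.0. Welch p is 0.165 and 0.228, so neither rejects, whereas the whole cohort at -23 rejects against D.

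**How often the verdicts differ.** The SE of the study mean is 17.2/sqrt(59) = 2.24. With the benchmarks held at their listed values, the chance that the mean falls in the band is about 4.5% at a true mean of -18.6 and about 39% at -23.5.

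**No SPSI effect, arm gap real.** A half-fused cohort has true mean (-17.5 - 19.7)/2 = -18.6, which is 1.1 points beyond D. Allowing for sampling error in the historical arm:
- Against D alone: P(Z < -1.96 + 1.1/2.45) = P(Z < -1.51) = 6.5%, against a nominal 2.5% in the favourable direction.
- Against D&F alone: P(Z < -1.96 - 1.1/2.51) = P(Z < -2.40) = 0.8%.
- Against D with 25% or 75% fused: about 4.1% or 9.9%.

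**No SPSI effect, arms truly equal.** Each comparison has its nominal 2.5%. The two statistics share the study mean, so their correlation is 5.014/(2.45 × 2.51) = 0.81. Both reject favourably in about 1.1% of studies, so at least one does in 2.5 + 2.5 - 1.1 = 3.9%.

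**The case against.** The strongest reply is that section 5.2 itself says most prior literature reports similar improvement with the two operations. In the 260/260 row the 2.2-point gap has SE sqrt(16.1²/260 + 18.3²/260) = 1.51, so z = 1.46 and p = 0.15. If the arms are equal, testing against one arm is not biased. That stands, and the 6.5% is conditional on a real gap. What remains is the multiplicity (3.9%) and the fact that the listed values, used as the plan would use them, still give opposite verdicts inside the band.

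It is also fair that sections 3 and 5.2 concede low power, that the search must precede analysis, and that section 5 has an independent statistician resolve discrepancies. These points limit the impact. They do not supply the missing rule, and section 5.2 keeps a formal rejection statement.

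A reader might infer three stronger things that the documents do not support:
- That no eligible control exists. Table 5 is a sampling of potential references, its rows carry no reference numbers, and the link to reference 26 is by label. A suitable randomized source may yet be listed.
- That the plan leaves open whether ODI level or ODI change decides. The t-test sentence names both, but the null and the rejection rule speak of improvement, and Table 5 lists change only.
- That the single-arm comparison is necessarily biased. This depends on a gap that the row does not establish.

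**Conclusion.** The point holds as a gap in the decision rule. One rejection statement covers a cohort mixing two operations, with no study, arm or conflict rule fixed and a control list that can be completed late. Neither 12-month row listed is shown to fit the plan's own description of its controls.

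On the illustrative row, the choice of arm decides the verdict for mean ODI changes across a band about 2.3 points wide. That rests on reading the brackets as SDs and on the assumed n, study SD and two-sided 5%. The false-claim figures also depend on the fused share and on whether the arm gap is real.

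The impact is modest: this is a secondary endpoint in a study that describes itself as a pilot, and neither the primary endpoint nor the sample size is touched. It lies between a minor clarification and a change that should be made. What favours making it is that it costs little and alters what can be concluded.

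**What to change.** 1. Reconcile the randomized-publications description with Table 5: either admit observational sources explicitly, or do not use the 260/260 row as a formal control.
2. Fix the eligibility rule and the control list before any 12-month outcome is summarised.
3. Replace the rejection rule with estimates and confidence intervals for change in ODI and NRS leg pain at 12 and 24 months, overall and by operation, set beside each listed D and D&F arm. State that the historical patients are not comparable, because operations here follow SPSI.
4. If the sponsor keeps a formal test, name one deciding comparison in advance, with its alpha and sidedness. Weighting the benchmark to the operations performed is possible, but it must carry the caveat that it removes part of any SPSI effect that acts through the choice of operation.

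The cost is a change of wording in section 5.2. The downsides are that literature found after the list is fixed can be shown only descriptively and that, under item 3, no formal claim is made on the secondary endpoint.

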### 5.3. Exploratory Endpoints

#### 5.3.1. Exploratory research question 1: Association between preoperative SPSI™ and the facet fluid sign

The facet fluid sign is observation of an abnormally wide area of high signal intensity in the left and/or right facet joints. Prior research has demonstrated that SPSI™ (labeled QSI in the paper) is significantly elevated in the presence of the facet fluid sign [31]. Data from the current study will be analyzed for supporting or refuting evidence to the prior observation. However, due to the expense of image transfer and independent radiologist assessment of the MRI exams, the observations by the investigators will be used. Each investigator will be provided with training material on how to interpret the facet fluid sign.

This training materials is based on training that was successfully used in the prior publication [31]. Analysis of variance tests (if data are normally distributed) or the Kruskal –Wallis equality-of-populations rank test will be used to test whether SPSI™ is significantly greater at levels identified by the investigators as having a facet fluid sign. This endpoint will be analyzed using the Safety Population.

#### **5.3.2. Exploratory research question 2: Proportion of levels treated using decompression only that have an increase in SPSI™ at 12 months**

As previously noted, one common justification for adding fusion surgery to surgery for decompression of lumbar stenosis, is that the decompression may create an instability that will later need to be treated. The fusion surgery is sometimes used prophylactically against the possibility of developing instability following decompression surgery. However, if instability rarely develops, this justification is not appropriate. Multiple research studies have been published providing data on the low-proportion of patients that develop instability following decompression-only surgery [7, 40, 49-54]. However, it is somewhat difficult to fully accept those studies since there are also scientific reviews concluding that there is currently no validated method for diagnosing instability [13]. Therefore, the proportion of patients where SPSI™ increases significantly following decompression-only surgery will be determined using an objective metric for spinal stability. This analysis will be completed as simple descriptive statistics and also using a simple test of proportions in comparison to the proportion of patients reported in prior publications. There is some evidence that a high translation-per-degree-of rotation can be associated with low-back symptoms [19]. In addition, there is some evidence that increased spondylolisthesis following decompression may be associated with worse outcomes [55, 56], so a binary classification (significantly increased SPSI™ versus no change in SPSI™) will be analyzed as a covariate when analyzing clinical outcome scores. If the change in SPSI™ is greater than +0.75, then that patient will be classified as having increased SPSI™. Otherwise, the patient will be classified as having no significant change. This endpoint will be analyzed using the Per-algorithm Population.

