Primary Endpoint	The primary endpoint is the proportion of lumbar spinal stenosis treatment plans that change when SPSI™ results are used in establishing the surgical plan.
Secondary Endpoints	The secondary endpoint is the comparison of clinical outcomes (as measured by ODI and NRS leg pain) at 12 months and 24 months in lumbar stenosis patients where the surgical plan was in accordance with the SPSI™ metric compared to historical controls.
Exploratory Endpoints	
 
• Does the presence of a facet fluid sign as indicated by the investigator on preoperative MRI correlate to instabilities specified by SPSITM results?
 
• What is the rate of instability (defined as a <math>> 1</math> standard deviation increase in SPSITM) 12 months after decompression (no fusion) surgery, how do these rates compare to the published data and does the development of post-decompression instability have an effect on the change in ODI or NRS scores relative to preop?
 
• What are the reoperation rates at 12 months following decompression alone and following decompression plus fusion, and how do these rates compare to published data from studies where similar inclusion and exclusion criteria were used and patients were randomized to decompression alone or decompression plus fusion?
 
• Does a nonunion following decompression plus fusion surgery have an effect on the change in ODI or NRS scores relative to preop?
 

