An objective metric called the Sagittal Plane Shear Index (SPSI™) has been recently described in the scientific literature [16]. This metric was labeled as the Quantitative Stability Index (QSI™) [16]. To avoid confusion between multiple intervertebral motion metrics, the metric that was previously labeled QSI™ is now being labeled as the Sagittal Plane Shear Index (SPSI™). The SPSI™ metric quantifies the sagittal plane intervertebral translation-per-degree-of-rotation (TPDR), and is reported as the number of standard deviations from the average found at radiographically normal levels in asymptomatic volunteers. The asymptomatic population that is used to define normal TPDR has been previously described [17]. Data for an additional 193 asymptomatic volunteers was added to this population to strengthen the definition of normal motion [18].

TPDR has previously been described as a potential metric for spinal instability [19], but was not extensively pursued following the 1990 publication for lack of a clinically practical and validated method measuring intervertebral translations and rotations in clinical practice. The SPSI™ metric can now be obtained in routine clinical practice using translation and rotation measurements obtained with validated computer-assisted methods (QMA®) [20-24]. SPSI™ is intended to be simple to use. According to the SPSI™ treatment planning algorithm,  $SPSI^{\text{TM}} > 2$  informs a clinician that the TPDR is  $> 2$  standard deviations above the average TPDR in the asymptomatic population. This provides for an objective diagnostic indicator for spinal instability defined as a specific, well-defined intervertebral motion metric that is outside the 95% confidence interval established for asymptomatic volunteers. If SPSI™ is  $> 2$  at a level where surgical treatment for stenosis is planned, then the clinician has objective evidence of abnormal motion and this may help to determine whether fusion should be completed in addition to the decompression surgery.

In conclusion: Spine fusion is used in addition to decompression surgery for lumbar spinal stenosis in order to prevent abnormal intervertebral motion causing associated symptoms. At the same time, if the intervertebral motion at the stenotic level is within normal limits prior to surgery, and it is unlikely that the decompression will compromise stability, only spinal decompression will be performed [25]. Fusion is not indicated if the spinal level is stable preoperatively.

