#### **4.1.4. Exploratory Endpoints**

The following exploratory endpoints will be assessed:

- Does the presence of a facet fluid sign as indicated by the investigator on preoperative MRI correlate to instabilities specified by SPSI™ results?
- What is the rate of instability (defined as a  $> 1$  standard deviation increase in SPSI™) 12 months after decompression (no fusion) surgery, how do these rates compare to the published data (for example Guha et al [40] and Cushnie et al [41] ), and does the development of post-decompression instability have an effect on the change in ODI or NRS scores relative to preop?
- What are the reoperation rates at 12 months following decompression alone and following decompression plus fusion, and how do these rates compare to published data from studies where similar inclusion and exclusion criteria were used and patients were randomized to decompression alone or decompression plus fusion [3, 42]?
- Does a nonunion following decompression plus fusion surgery have an effect on the change in ODI or NRS scores relative to preop ?

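### Exploratory question 2 has two cut-offs for a rise in SPSI at 12 months: more than 1 SD in the endpoint definition, more than 0.75 SD in the analysis section

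*Combined protocol and SAP*

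**What the plan says.** Section 4.1.4 poses the question as "What is the rate of instability (defined as a $> 1$ standard deviation increase in SPSI™") at 12 months in subjects decompressed without fusion. The synopsis gives the same definition. In the same item, section 4.1.4 goes on to ask: "does the development of post-decompression instability have an effect on the change in ODI or NRS scores relative to preop".

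Section 5.3.2 is the analysis text for this question and has two parts.

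- **Rate.** "the proportion of patients where SPSI™ increases significantly following decompression-only surgery will be determined using an objective metric for spinal stability". This is to be described and also compared with published proportions. The sentence gives no number.
- **Effect on outcome scores.** "a binary classification (significantly increased SPSI™ versus no change in SPSI™) will be analyzed as a covariate when analyzing clinical outcome scores". The rule for the class follows: "If the change in SPSI™ is greater than +0.75, then that patient will be classified as having increased SPSI™". All other patients count as having no significant change.

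On units, section 1.1 says that the metric "is reported as the number of standard deviations from the average found at radiographically normal levels in asymptomatic volunteers". Section 1.2 describes the same scaling.

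**The concern.** Both texts concern the same question, the same decompression-only group and the same 12-month time point, but the numerical rules differ. A patient whose SPSI rises by more than 0.75 and up to 1.0 is increased under section 5.3.2 and not unstable under the endpoint definition.

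Two things are at stake. First, with both values in the current text, an analyst could choose between them after seeing the 12-month data and still claim to follow the protocol. Second, if the rate were taken at 1 SD and the covariate at 0.75, the reported rate of instability and the reported effect of instability on ODI and NRS would describe different groups of patients.

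The rate also carries an argument. Section 5.3.2 uses it to judge whether fusion as a precaution against later instability is justified, and the study is meant to inform the design of later research.

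**Working it through.** **Step 1: a common scale.** SPSI is a number of reference-population standard deviations (sections 1.1 and 1.2). A rise of 1 SD is therefore +1.0 on the SPSI scale, and +0.75 is 0.75 SD. The cut-offs differ by 1.0 − 0.75 = 0.25. Reading 1 standard deviation as the SD of the study sample has no support in the text, and nothing indicates that such an SD would equal 0.75.

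**Step 2: which analyses conflict.**

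| Use | Synopsis and 4.1.4 | 5.3.2 | Status |
|---|---|---|---|
| Effect on change in ODI/NRS | instability, > 1 SD | covariate, > +0.75 | explicit conflict |
| Rate at 12 months | instability, > 1 SD | significant increase, no number given | conflict by inference |

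The inference for the rate rests on two facts: the covariate class carries the same label of significant increase, and +0.75 is the only cut-off in section 5.3.2.

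**Step 3: size.** The plan derives no figure from either cut-off, so there is nothing to reproduce. It also gives no mean, SD or distribution for the change in SPSI. As an assumption, take the change as normal with mean m and standard deviation s. The share above cut-off c is P = 1 − Φ((c − m)/s).

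Example, m = 0 and s = 0.5: at 0.75, 1 − Φ(1.5) = 6.7%; at 1.0, 1 − Φ(2.0) = 2.3%.

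| m | s | > 0.75 | > 1.0 | Difference (points) | Ratio |
|---|---|---|---|---|---|
| 0 | 0.5 | 6.7% | 2.3% | 4.4 | 2.94 |
| 0 | 0.75 | 15.9% | 9.1% | 6.7 | 1.74 |
| 0 | 1.0 | 22.7% | 15.9% | 6.8 | 1.43 |
| 0.25 | 0.5 | 15.9% | 6.7% | 9.2 | 2.37 |
| 0.25 | 0.75 | 25.2% | 15.9% | 9.4 | 1.59 |
| 0.25 | 1.0 | 30.9% | 22.7% | 8.2 | 1.36 |
| 0.5 | 0.5 | 30.9% | 15.9% | 15.0 | 1.94 |
| 0.5 | 0.75 | 36.9% | 25.2% | 11.7 | 1.46 |
| 0.5 | 1.0 | 40.1% | 30.9% | 9.3 | 1.30 |

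Differences and ratios are taken before rounding.

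**Step 4: share of the increased group that misses the endpoint.** This is 1 − 1/ratio. It runs from 1 − 1/2.94 = 66% (m = 0, s = 0.5) down to 1 − 1/1.30 = 23% (m = 0.5, s = 1.0).

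**Step 5: subjects.** The number treated by decompression alone is not given. Assume 20 to 45 of the 65, all analysable at 12 months. At m = 0, the number changing class runs from 20 × 0.044 = 0.9 to 45 × 0.068 = 3.1. The maximum over the table is 45 × 0.150, or about 6.7.

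**Step 6: reach.** The sample size in section 5.5 rests on 10% against 25% of surgical plans changed. Neither cut-off enters it.

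**The case against.** The strongest defence is that the two numbers serve different purposes. Section 5.3.2 never calls a rise of 0.75 instability; it calls it increased SPSI. On that reading the rate takes the endpoint's 1 SD and the covariate deliberately uses a lower threshold. This would remove the conflict for the rate, which is why that part is described only as an inference. It does not help the covariate, because section 4.1.4 asks the ODI/NRS question about the instability it has just defined. It would also leave rate and covariate on different groups without saying so.

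A second objection is that +1.0 has no more rationale in the document than +0.75, and that section 5.3.2 is the operative analysis text. That is fair as far as it goes: the document does not show which value was intended. The default to +1.0 follows only from the definition being stated twice as the endpoint, and +0.75 remains open to the sponsor.

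Third, the sizes are assumed. That stands. With s widened to 1.5 and m = 0.5, the shares are 43.4% and 36.9% and the ratio falls to 1.17. The count of about 7 subjects needs the largest assumed group and the most favourable cell together. It also ignores subjects whose 12-month SPSI cannot be analysed, for whom section 5.7 plans no imputation.

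Fourth, section 5 has the analysis done twice, with an independent statistician resolving discrepancies. That limits unreviewed choice by one analyst, but it does not say which text governs.

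**Conclusion.** The concern holds. For the ODI/NRS covariate the plan contradicts its own endpoint definition; for the rate, the same contradiction is the likelier reading but not the only one. This part rests on the text alone and needs no distributional assumption.

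The practical size does rest on assumptions. With a normal change, mean 0 to +0.5 and SD 0.5 to 1.0, the lower cut-off adds 4.4 to 15.0 percentage points to the share classified. In subjects that is about 1 to 3 at mean 0 and about 7 at most, if 20 to 45 are treated by decompression alone. The numbers are small, but so is the group they would enter.

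The matter should be corrected but does not threaten the trial. It is confined to one exploratory endpoint; the primary endpoint, the sample size and the safety analysis are not affected.

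**What to change.** Before the 12-month data are analysed, reconcile the synopsis, section 4.1.4 and section 5.3.2 to one pre-specified cut-off, and state in 5.3.2 that it applies to both the rate and the ODI/NRS covariate. By default, put +1.0 in section 5.3.2. If the sponsor prefers +0.75, record the rationale and amend the synopsis and section 4.1.4 instead. Report the result at the other cut-off as one sensitivity row.

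The cost is a wording change in one section (two if +0.75 is kept) and one extra tabulated row. No new data and no change in sample size are needed. Moving to +1.0 leaves fewer subjects in the increased group of an exploratory comparison that is already small.
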